15.1.2 Adverse Events Leading to Discontinuation of Study Intervention

A listing of TEAEs leading to discontinuation of study intervention, or discontinuation of study, if any, will be provided.

The frequency (number and percentage) of participants with TEAEs leading to permanent discontinuation of each study intervention by study intervention will also be provided in a table.

15.2 Deaths, Other Serious Adverse Events, and Other Significant Adverse Events

15.2.1 Deaths

A listing of deaths, if any, will be provided.

15.2.2 Serious Adverse Events

A listing of serious AEs (SAEs), if any, will be provided.

Summary table of the number and percentage of participants with at least one SAE by SOC and PT will also be provided.

15.2.3 Other Significant Adverse Events

The following AESI were defined:

- Infections (serious, severe, and opportunistic, \geq Grade 3)
- Seizures
- Elevated lipase, elevated amylase, pancreatitis
- Liver-related events

More information can be found in the CSP, Section 8.3.7.

AESI will be identified in the AE listings. Summary table of the number and percentage of participants with at least one AESI by SOC and PT will also be provided.

15.3 Clinical Laboratory Evaluation

Listings and summary statistics at each assessment time will be presented using the Système International (SI) units. Normal ranges will be provided by the laboratory department, and out of range flags will be calculated based on the normal ranges. Laboratory data not transferred from the central laboratory in SI units will be converted to SI units before processing. Both original units and SI units will be provided in the SDTM domain.

Safety laboratory parameters are separated into:

- Hematology (including coagulation)
- Biochemistry
- Urinalysis
- Other tests

Hematology, biochemistry, and coagulation will be summarized by study intervention and time point using descriptive statistics for baseline (see definition in Section 9), each evaluation during the study, and change from baseline to each evaluation.

Listings of abnormal test results (low and high) will also be provided.

15.4 Vital Signs

Vital signs data will be summarized by study intervention and time point using descriptive statistics for baseline (see definition in Section 9), each evaluation during the study, and change from baseline to each evaluation. Listing of vital signs data will be provided.

Vital sign summaries will include all vital sign assessments from the on-treatment period. All vital sign assessments will be listed, and those collected outside the on-treatment period will be flagged in the listing.

15.5 Other Safety or Tolerability Evaluations

Safety ECG data will be summarized by study intervention and time point using descriptive statistics for baseline (see definition in Section 9), each evaluation during the study, and change from baseline to each evaluation. Listing of safety ECG data will be provided.

ECG summaries will include all ECG assessments from the on-treatment period. All ECG assessments will be listed.

The analysis of QT data is complicated by the fact that the QT interval is highly correlated with heart rate. Because of this correlation, formulas are routinely used to obtain a corrected value, denoted QTc, which is independent of heart rate. This QTc interval is intended to represent the QT interval at a standardized heart rate. Several correction formulas have been proposed in the literature. The QT interval will be corrected for heart rate by the Fridericia's formula, QTcF, is defined as

$$QTcF = \frac{QT}{\sqrt[3]{RR}} ,$$

where RR represents the RR interval of the ECG, in seconds, and can be estimated as 60/Heart Rate.

Investigator reported interpretation results will also be tabulated by study intervention and time point using the number and percentage of participants for each interpretation category (Normal, Abnormal Not Clinically Significant [NCS], Abnormal Clinically Significant [CS]).

16 Analyses of Other Endpoints/Estimands

16.1 Pharmacokinetics

PK evaluation will be performed by Nuvisan GmbH.

All statistical analyses and descriptive summaries of PK data will be performed on the PK Analysis Set.

16.1.1 Descriptive Statistics of PK Concentration Data

PK measurements of digoxin, metformin, and rosuvastatin in plasma of Part 1 and sumatriptan in plasma of Part 2 as well as evobrutinib (and metabolite, if available) in plasma of Part 1 and Part 2 will be descriptively summarized using: number of non-missing observations (n), arithmetic mean (Mean), standard deviation (SD), coefficient of variation (CV%), minimum (Min), median (Median) and maximum (Max).

Descriptive statistics will only be calculated for $n > 2$ in which a measurement of below lower limit of quantification (BLQ) represents a valid measurement and will be taken as zero for summary statistics of PK concentration data.

Any mean or median value that is below the lower limit of quantification will be shown as BLQ.

Descriptive statistics of PK concentration data will be calculated using values with the same precision as the source data and rounded for reporting purposes only. In export datasets, as well as in the SDTM PC domain, PK concentrations will be provided with full precision and will not be rounded.

The following conventions will be applied when reporting descriptive statistics of PK concentration data:

n	0 decimal place
Mean, Min, Median, Max:	3 significant digits
SD:	4 significant digits
CV%:	1 decimal place

16.1.2 Descriptive Statistics of PK Parameter Data

PK parameter data of digoxin, metformin, and rosuvastatin in plasma and metformin in urine each on Day 1 and Day 10 of Part 1 and sumatriptan in plasma on Day 1 and Day 8 of Part 2 using: number of non-missing observations (n), arithmetic mean (Mean), standard deviation (SD), coefficient of variation (CV%), minimum (Min), median (Median), maximum (Max), geometric mean (GeoMean), the geometric coefficient of variation (GeoCV) and the 95% confidence interval for the GeoMean (LCI 95% GM, UCI 95% GM). For PK parameters related to time (e.g. t_{max} , t_{lag} , t_{last}), only n, Min, Median, and Max may be reported.

Descriptive statistics will only be calculated for a PK parameter when $n > 2$.

[figure not shown]
PK parameters read directly from the measurements (i.e. C_{max}) will be reported with the same precision as the source data. All other PK parameters will be reported to 3 significant figures. In export datasets, as well as in the SDTM PP domain, PK parameters will be provided with full precision and will not be rounded. Descriptive statistics of PK parameter data will be calculated using full precision values and rounded for reporting purposes only.

The following conventions will be applied when reporting descriptive statistics of PK parameter data:

n	0 decimal place
Mean, Min, Median, Max, GeoMean, 95% CI:	3 significant digits
SD:	4 significant digits
CV%, GeoCV%:	1 decimal place

16.1.3 Statistical Analysis of PK Parameter Data

Part 1

- **Analysis of Primary Endpoints**

A general linear model with a fixed effect for TREATMENT and a random effect for SUBJECT will be applied to log-transformed PK parameters C_{max} and $AUC_{0-\infty}$ based on the PK analysis set to assess the effect of multiple doses of evobrutinib on the PK of the transporter substrates digoxin, metformin, and rosuvastatin. Treatment differences on the log scale of transporter substrates with evobrutinib vs substrates alone (Day 10 versus Day 1) will be estimated for C_{max} and $AUC_{0-\infty}$ together with their 90% CIs.

Point estimates and CIs will be back transformed to the original scale.

- **Analysis of Secondary Endpoints**

[figure not shown]
The same analysis model as described for the primary endpoints will be provided for the secondary endpoint $AUC_{0-t_{last}}$ of transporter substrates.

The same analysis model as described for the primary endpoints will be provided for the secondary endpoint CL_R of metformin only.

Sensitivity Analyses

The same analyses on the primary and secondary endpoints will be repeated including participants
CCI

Part 2

- **Analysis of Primary Endpoints**

A general linear model with a fixed effect for TREATMENT and a random effect for SUBJECT will be applied to log-transformed PK parameters C_{max} and $AUC_{0-\infty}$ based on the PK analysis set to assess the effect of multiple doses of evobrutinib on the PK of the transporter substrate sumatriptan. Treatment differences on the log scale of sumatriptan with evobrutinib vs sumatriptan alone (Day 8 versus Day 1) will be estimated for C_{max} and $AUC_{0-\infty}$ together with their 90% CIs.

Point estimates and CIs will be back transformed to the original scale.

- **Analysis of Secondary Endpoints**

The same analysis model as described for the primary endpoints will be provided for the secondary endpoint $AUC_{0-t_{last}}$ of sumatriptan.

Sensitivity Analyses

The same analyses on the primary and secondary endpoints will be repeated including participants
CCI

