4.2 Scientific Rationale for Study Design

The study design and endpoints are typical for a DDI study of this type. The effect of evobrutinib on transporter activities will be investigated by measurement of the PK of the transporter substrates digoxin, metformin, rosuvastatin, and sumatriptan. Oral administration of the probe drug transporter substrates is expected to be a sensitive test for potential interactions with drug transporters such as P-gp, MATE1/MATE2-K, BCRP, and OCT1 since they reflect effects on both presystemic and systemic clearance. The transporter substrate cocktail (digoxin, metformin, and rosuvastatin) will be administered during Part 1 of the study as a reference treatment on Day 1 followed on Day 4 through Day 12 by multiple doses of evobrutinib twice daily, with a second dose of substrate cocktail given with the morning dose of evobrutinib on Day 10. During

Part 2, sumatriptan will be administered on Day 1 as reference and on Day 8, and evobrutinib will be administered twice daily on Days 2 through 8.

A single-sequence design for Part 1 and Part 2 was chosen because the exact mechanism of inhibition of the transporters by evobrutinib and therefore the time course of on- / offset of these effects are not known. Therefore, evobrutinib will be administered twice daily for 6 days before the second administration of transporter substrates in each study part.

The transporter substrate cocktail to be used in Part 1 of this study (digoxin [0.25 mg], metformin [10 mg] and rosuvastatin [10 mg]) has been optimized as a screening tool for transporter mediated DDIs (Wiebe 2020, Stopfer 2018) based on PK analyses of the substrates both separately and in combination. The safety profiles of the individual substrates of the cocktail are well established since these drugs are routinely used in clinical practice. Stopfer reported mild or moderate adverse events in 15 of 30 participants (Stopfer 2018). Similarly, for Part 2, sumatriptan (25 mg) has been recommended and used as a substrate for determining PK effects of potential OCT1 effectors (Chu 2018). The safety profile of sumatriptan is well established since it is routinely used in clinical practice (Sumatriptan SmPC).

Because some of the transporters to be investigated in this study might exist as polymorphic variants, which could affect the interpretation of the study results, samples for CCI [REDACTED] will be collected and analyzed.

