- Urine will be collected for metformin analysis (as it is 100% eliminated by renal excretion) on Days 1 to 2 and Days 10 to 11 and an aliquot will be taken from each collection interval for concentration measurements ([Table 1](#)). The volume of urine from each collection interval will be measured.

Part 2

- Whole blood samples of approximately 2 mL for measurement of plasma concentrations of sumatriptan will be collected on Days 1 to 2 and Days 8 to 9 (Table 2).
- Whole blood samples of approximately 2 mL for measurement of plasma concentrations of evobrutinib will be collected on Days 6, 7, and 8 (Table 2).

Collection times are specified in the Schedule of Assessments (Section 1.3). The actual date and time (24-hour clock time) of each sample will be recorded to calculate actual time elapsed since the prior dose administration. For urine samples, the actual start and end date and time (24-hour clock time) of each urine fraction, as well as the volume of each urine collection fraction, will be recorded.

- The quantification of evobrutinib, digoxin, metformin, rosuvastatin, and sumatriptan in plasma samples, and metformin in urine samples, will be performed using fully validated assay methods. Concentrations will be used to evaluate the PK parameters of the transporter substrates, and evobrutinib concentrations will be summarized.
- Remaining samples collected for analyses of evobrutinib and transporter substrate concentrations may also be used to evaluate safety or efficacy aspects related to concerns arising during or after the study. Additionally, remaining plasma samples may be used for investigation of evobrutinib or transporter substrate metabolites.
- Details on processes for collection and handling of these samples are in the Laboratory Manual. Retention time and possible analyses of samples after the End of Study are specified in the respective ICF.
- PK parameters will be derived using noncompartmental methods with the validated computer program Phoenix® WinNonlin® (version 6.4 or higher; Certara, L.P., Princeton, New Jersey, USA).

The exact date and time of sample collection and study intervention administration (24-hour clock time) must be recorded in the eCRF and will be used in the calculation of PK parameters. The accepted time deviations from planned PK sampling times that will not be considered a protocol violation are listed in Table 4.

Table 4 PK Sampling Time Windows

Procedure	Time Point (Relative Time)	Window Allowance

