To characterize the effect of evobrutinib on digoxin, metformin, and rosuvastatin (Part 1), and sumatriptan (Part 2) secondary PK parameters in healthy participants	
Plasma PK parameters (Part 1 and Part 2): t_{max}, $t_{1/2}$, and $AUC_{0-tlast}$, CL/F, and Vz/FUrine PK parameters (Part 1, metformin only): Ae_{0-36} and CL_R

CCI

CL/F=apparent total body clearance, CL_R=renal clearance, ECG= electrocardiogram, PK=pharmacokinetics, TEAE=treatment-emergent adverse event, Vz/F= apparent volume of distribution.

6 Overview of Planned Analyses

The final, planned analyses identified in the CSP and in this IAP will be performed after the last participant has completed the last visit and after all data queries resolved as well as the database locked.

A data review meeting will be held prior to database lock for the final analysis. In addition, no database can be locked until this IAP has been approved.

7 Changes to the Planned Analyses in the Clinical Study Protocol

There are no changes to the planned analyses in the clinical study protocol.

8 Analysis Sets and Subgroups

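### Four secondary PK endpoints (tmax, t1/2, Vz/F, metformin Ae0-36) are summarised by day only, so no within-participant confidence interval for evobrutinib's effect is planned, and for tmax no between-day contrast at all

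*SAP*

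**What the plan says.** SAP 5 (Objectives and Endpoints) gives the secondary PK objective as "To characterize the effect of evobrutinib on digoxin, metformin, and rosuvastatin (Part 1), and sumatriptan (Part 2) secondary PK parameters in healthy participants". The endpoints listed are tmax, t1/2, AUC0-tlast, CL/F and Vz/F in plasma (both parts), and Ae0-36 and CLR in urine (metformin, Part 1).

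SAP 16.1.3 fits a log-scale model with a fixed treatment effect and a random subject effect. Among the secondary endpoints it extends the model to three cases:

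- Part 1, AUC0-tlast: the model "will be provided for the secondary endpoint $AUC_{0-t_{last}}$ of transporter substrates".
- Part 1, metformin: "The same analysis model as described for the primary endpoints will be provided for the secondary endpoint CL_R of metformin only".
- Part 2: the model "will be provided for the secondary endpoint $AUC_{0-t_{last}}$ of sumatriptan".

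Protocol 9.4.3 has the same list, and SAP 7 declares no change from the protocol.

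Everything else is covered by SAP 16.1.2 and 16.1.6.1. These provide descriptive statistics per analyte and study day, including a geometric mean with a 95% CI for each day. For time parameters such as tmax, "only n, Min, Median, and Max may be reported". Boxplots and spaghetti plots (SAP 16.1.6.2) are limited to the primary parameters. SAP 9 says in general terms that with- versus without-evobrutinib comparisons will be presented, but ties this to no parameter or method.

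**The concern.** The objective concerns an effect, and each participant supplies both a reference and a test profile, so the natural estimate is a within-participant contrast. For four of the seven endpoints the plan gives two separate columns of statistics instead. The interval attached to each column describes one day's geometric mean. It carries between-participant variability and says nothing about how precisely the change between days is known.

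This bears on interpretation. Protocol 4.2 favours oral probes "since they reflect effects on both presystemic and systemic clearance". If a substrate's AUC changes, a reader will look at t1/2 and tmax for clues about which of the two is involved. For metformin, which Protocol 8.4 describes in these terms: "as it is 100% eliminated by renal excretion", the reader will look at the amount excreted. Those are the parameters without an interval for the change.

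**Working it through.** The plan states no figure on this point, and the precision section is blacked out. The check is therefore an inventory, followed by a sizing under stated assumptions.

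**1. Inventory of the seven secondary PK endpoints**

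| Endpoint | Planned between-day estimate with CI? | Derivable from modelled output? |
|---|---|---|
| AUC0-tlast | Yes | n/a |
| CLR (metformin) | Yes | n/a |
| CL/F | No | Yes, fully: CL/F = Dose/AUC0-inf, so ratio and CI are the inverse of those for AUC0-inf |
| t1/2 | No | No |
| Vz/F | No | Point ratio only, once the t1/2 ratio is known: Vz/F = Dose/(AUC0-inf × λz), so ratio(Vz/F) = ratio(t1/2)/ratio(AUC0-inf); the CI does not follow |
| Ae0-36 (metformin) | No | CI no: CLR = Ae0-36/AUC0-36, and AUC0-36 is not modelled |
| tmax | No | No |

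**2. What the daily tables give for the log-scale parameters.** With the same participants on both days, the ratio of the two geometric means equals the paired model's point estimate. The PK analysis set requires the primary endpoints on both days, and AUC0-inf needs λz, so pairs for t1/2 and Vz/F should be essentially complete. Ae0-36 pairs may not be, since SAP 16.1.4 allows urine parameters to go uncalculated when collections are missing or incomplete. The paired CI cannot be recovered, because the same two columns fit any within-participant correlation. This assumes t1/2 is not treated as one of the time parameters with the reduced summary; the SAP's examples of these do not include it.

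**3. Size for a log-scale parameter.** Inputs: n = 16 (approximate evaluable number per part, Protocol 1.1). Assumed: between-participant SD b = 0.3 to 0.4 and within-participant SD w = 0.15 to 0.25, both on the log scale.

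- Paired 90% half-width: t(0.95, 15) × w × √(2/16) = 1.753 × w × 0.3536.
  - w = 0.15: 0.093, so ×/÷ 1.10.
  - w = 0.25: 0.155, so ×/÷ 1.17.
- Daily summaries read as unpaired: t(0.95, 30) × √(2(b² + w²)/16) = 1.697 × √(b² + w²) × 0.3536.
  - b = 0.3, w = 0.15: 0.201, so ×/÷ 1.22.
  - b = 0.4, w = 0.25: 0.283, so ×/÷ 1.33.
- Ratio of half-widths: 1.51 (b = 0.3, w = 0.25) to 2.76 (b = 0.4, w = 0.15).

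These SDs imply correlations b²/(b² + w²) of 0.59 to 0.88. Over a wider range, with an assumed daily geometric CV of 40%, a true ratio of 1 and n = 16, the unpaired reading is 0.79 to 1.26, against:

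| Correlation | Paired 90% CI | Unpaired/paired log width |
|---|---|---|
| 0 | 0.79 to 1.27 | 0.97 |
| 0.3 | 0.82 to 1.22 | 1.16 |
| 0.5 | 0.84 to 1.18 | 1.37 |
| 0.7 | 0.88 to 1.14 | 1.77 |
| 0.9 | 0.93 to 1.08 | 3.06 |

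The width ratios are the same at CVs of 30% and 50%.

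**4. tmax.** A constructed example of 16 participants, using scheduled sampling times:

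- Without evobrutinib: 0.67 h (1 participant), 1 h (6), 1.5 h (3), 3 h (3), 4 h (3).
- With evobrutinib: the six at 1 h move to 1.5 h, the three at 3 h move to 4 h, and the rest are unchanged.

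Both days have median 1.5 h, minimum 0.67 h and maximum 4 h, so the planned table is identical for the two. Yet nine participants increased, none decreased, and the paired Hodges-Lehmann shift is 0.25 h.

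**The case against.** The best case for the plan is that it is a consistent, pre-specified choice. Protocol and SAP agree, the objective says characterise, and Protocol 9.1 calls the analysis purely descriptive. No objective asks to apportion an effect between absorption and clearance; Protocol 4.2 mentions both only to explain why oral probes are sensitive. This limits the weight of the point but does not remove it. Ruling out hypothesis tests does not rule out estimation, and the plan already gives ratios with 90% CIs for two secondary endpoints.

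Three stronger readings are tempting, and the documents do not support them.

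- *No effect is estimated for these endpoints.* Too strong for t1/2, Vz/F and Ae0-36, where the daily geometric means yield a point ratio on complete pairs. Only tmax lacks a readable contrast.
- *The pairing is discarded.* True of the summary tables only. SAP 16.1.6.1 lists individual parameters by participant and day. SAP 16.1.6.2 plans overlaid concentration plots by participant, which most naturally puts both days on one plot. Paired results could be computed later; they are not pre-specified.
- *An unchanged metformin AUC could hide a fall in renal clearance.* If elimination is wholly renal, ratio(AUC) = ratio(Ae)/ratio(CLR), so 0.80/0.80 = 1.00 is possible. But CLR is itself modelled with a 90% CI and would show 0.80, so nothing is hidden. An Ae0-36 interval would only help judge the offsetting change in absorption.

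It is also fair to say that the unpaired comparison is planned nowhere. It stands for what a reader might do with the tables, and the SDs behind it are assumptions.

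**Conclusion.** The point holds in a limited form. For tmax, t1/2, Vz/F and metformin Ae0-36, the secondary objective is served only by daily summaries. What is missing is a within-participant confidence interval for t1/2, Vz/F and Ae0-36, and any between-day contrast for tmax. Where correlation is moderate to high, a reader working from the tables would face an interval roughly 1.5 to 2.8 times as wide on the log scale as the design can deliver; at low correlation there is little or no gain. These multiples rest on assumed SDs and on 16 complete pairs.

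The primary analysis, the sample size and the modelled metformin CLR are untouched. The documents give no ground for requiring any particular rule for reading transporter effects from these parameters. Severity is low: an optional, inexpensive improvement.

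**What to change.** In SAP 16.1.3, add t1/2 and Vz/F (all substrates, both parts) and Ae0-36 (metformin, Part 1) to the same log-scale paired model, reporting Day 10/Day 1 or Day 8/Day 1 ratios with 90% CIs. For tmax, report the paired Hodges-Lehmann median difference with a 90% CI. Label all of these descriptive. If the sponsor prefers not to, one sentence saying that these four endpoints are summarised by day only would bring the stated analysis into line with the objective.

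The cost is a few more runs of existing model code, one nonparametric calculation and one more table per part. No new data, samples or participants are needed. The downside is a few more exploratory intervals to read.
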